### **QoL/function improvement rate**

The QoL/function improvement rate will be defined as the number (%) of patients with 2 consecutive assessments at least 14 days apart that show a clinically meaningful improvement (an increase from baseline score  $\geq 10$  for EORTC QLQ-C30 functional scales and global health status/QoL) in that scale from baseline.

The denominator will consist of a subset of the ITT population who have a baseline QoL/function score of  $\leq 90$ .

### 11.3.1.2 LC13

The LC13 is a lung cancer specific module from the EORTC comprising 13 questions to assess lung cancer symptoms (cough, haemoptysis, dyspnoea and site-specific pain), treatment-related side-effects (sore mouth, dysphagia, peripheral neuropathy and alopecia) and pain medication. The LC13 incorporates symptom scales including:

- Dyspnoea (multi-item scale based on 3 questions: were you short of breath when you rested; walked; climbed stairs)
- Cough: 1 item (how much did you cough?)
- Haemoptysis: 1 item (did you cough up blood?)
- Pain: 3 individual items (Have you had pain in your chest; your arm or shoulder; other parts of your body?)

The dyspnoea scale is only used if all 3 items have been scored; otherwise the items are treated as single-item measures. The scoring approach for the LC13 is identical in principle to that for the symptom scales/single items of the EORTC QLQ-C30.

#### Definition of clinically meaningful changes

Changes in score compared with baseline will be evaluated. A minimum clinically meaningful change is defined as an absolute change in the score from baseline of  $\geq 10$  for scales/items from the LC13 (Osoba et al 1998). For example, a clinically meaningful deterioration or worsening in chest pain (as assessed by LC13) is defined as an increase in the score from baseline of  $\geq 10$ , whereas a clinically meaningful improvement is defined as a decrease in the score from baseline of  $\geq 10$ . At each post-baseline assessment, the change in symptoms from baseline will be categorised as improvement, no change or deterioration as shown in Table 13.

**Table 13 Visit Response for HRQoL and disease-related symptoms**

Score	Change from baseline	Visit response
LC13 symptom scales/items	$\geq +10$	Deterioration
	$\leq -10$	Improvement
	Otherwise	No change

HRQoL Health Related Quality of Life; LC13 Lung Cancer Module.

#### Time to symptom deterioration

For each of the symptoms scales/items in LC13, time to symptom deterioration will be defined as the time from the date of randomisation until the date of the first clinically meaningful symptom deterioration (an increase in the score from baseline of  $\geq 10$ ) or death (by any cause) in the absence of a clinically meaningful symptom deterioration, regardless of whether the

patient withdraws from study drug or receives another anticancer therapy prior to symptom deterioration. Death will be included as an event only if the death occurs within 2 visits of the last PRO assessment where the symptom change could be evaluated.

Patients whose symptoms (as measured by LC13) have not shown a clinically meaningful deterioration and who are alive at the time of the analysis will be censored at the time of their last PRO assessment where the symptom could be evaluated. Also, if symptoms deteriorate after 2 or more missed PRO assessment visits or the patient dies after 2 or more missed PRO assessment visits, the patient will be censored at the time of the last PRO assessment where the symptom could be evaluated. If a patient has no evaluable visits or does not have baseline data they will be censored at Day 1.

The population for the analysis of time to symptom deterioration will include a subset of the ITT population who have baseline scores of  $\leq 90$ .

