### **Time to QoL/Function deterioration**

For QoL, time to deterioration will be defined as the time from the date of randomisation until the date of the first clinically meaningful deterioration (a decrease in the function scales or the global health status/QoL from baseline of  $\geq 10$ ) or death (by any cause) in the absence of a clinically meaningful deterioration, regardless of whether the patient withdraws from study drug or receives another anticancer therapy prior to QoL/function deterioration. Death will be included as an event only if the death occurs within 2 visits of the last PRO assessment where the QoL/function change could be evaluated.

Patients whose QoL (as measured by EORTC QLQ-C30) have not shown a clinically meaningful deterioration and who are alive at the time of the analysis will be censored at the time of their last PRO assessment where the QoL/function could be evaluated. Also, if QoL deteriorates after 2 or more missed PRO assessment visits or the patient dies after 2 or more missed PRO assessment visits, the patient will be censored at the time of the last PRO assessment where QoL/function could be evaluated. If a patient has no evaluable visits or does not have baseline data they will be censored at Day 1.

The population for the analysis of time to QoL/function deterioration will include a subset of the ITT population who have baseline scores of  $\geq 10$ .

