3.2.1.2 Progression free survival (PFS)

PFS (per RECIST 1.1 as assessed by BICR) will be defined as the time from the date of randomisation until the date of the first objective disease progression or death (by any cause in the absence of progression) regardless of whether the patient withdraws from randomised therapy or receives another anti-cancer therapy prior to progression (i.e., date of PFS event or censoring – date of randomisation + 1). Patients who have not progressed or died at the time of analysis will be censored at the time of the latest date of assessment from their last RECIST 1.1 assessment. However, if the patient progresses or dies after 2 or more missed visits, the patient will be censored at the time of the latest RECIST 1.1 assessment prior to the two missed visits.

Given the scheduled visit assessment scheme (ie eight-weekly for the first 48 weeks then twelve-weekly thereafter) the definition of 2 missed visits will change. If the previous RECIST assessment is less than study day 274 (ie week 39) then two missing visits will equate to 18 weeks since the previous RECIST assessment, allowing for early and late visits (ie, 2 x 8 weeks + 1 week for an early assessment + 1 week for a late assessment = 18 weeks). If the two missed visits occur over the period when the scheduled frequency of RECIST assessments changes from eight-weekly to twelve-weekly this will equate to 22 weeks (ie,

take the average of 8 and 12 weeks which gives 10 weeks and then apply same rationale hence 2×10 weeks + 1 week for an early assessment + 1 week for a late assessment = 22 weeks). The time period for the previous RECIST assessment will be from study days 274 to 344 (ie week 39 to week 49). From week 49 onwards (when the scheduling changes to twelve-weekly assessments), two missing visits will equate to 26 weeks (ie 2×12 weeks + 1 week for an early assessment + 1 week for a late assessment = 26 weeks). If the patient has no visits or does not have baseline data they will be censored at study day 1 unless they die within 2 visits of baseline (16 weeks plus 1 week allowing for a late assessment within the visit window).

The PFS time will always be derived based on scan/assessment dates not visit dates.

PFS will also be obtained using the algorithm described above for the RECIST site investigator tumour data.

RECIST 1.1 assessments/scans contributing towards a particular visit may be performed on different dates. The following rules will be applied:

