3.3.1.1 Time to symptom deterioration

For each of the symptoms scales/items in the EORTC-QLQ-C30, time to symptom deterioration will be defined as the time from randomisation until the date of the first clinically meaningful symptom deterioration (an increase in the score from baseline of ≥ 10) or death (by any cause) in the absence of a clinically meaningful symptom deterioration, regardless of whether the patient withdraws from study treatment or receives another anticancer therapy prior to symptom deterioration (i.e. date of symptom deterioration event or censoring whichever is earlier – date of randomisation + 1). Death will be included as an event only if the death occurs within 2 visits of the last PRO assessment where the symptom change could be evaluated.

Patients whose symptoms (as measured by EORTC-QLQ-C30) have not shown a clinically meaningful deterioration and who are alive at the time of the analysis will be censored at the time of their last PRO assessment where the symptom could be evaluated. Also, if symptoms deteriorate after 2 or more missed PRO assessment visits or the patient dies after 2 or more

missed PRO assessment visits, the patient will be censored at the time of the last PRO assessment where the symptom could be evaluated (prior to the two missed assessment visits). Given the scheduled visit assessment scheme (ie eight-weekly for the first 48 weeks then twelve-weekly thereafter) the definition of 2 missed visits will change. If the previous PRO assessment is less than study day 274 (ie week 39) then two missing visits will equate to 18 weeks since the previous PRO assessment, allowing for early and late visits. If the two missed visits occur over the period when the scheduled frequency of PRO assessments changes from eight-weekly to twelve-weekly this will equate to 22 weeks. The time period for the previous PRO assessment will be from study days 274 to 344 (ie week 39 to week 49). From week 49 onwards, two missing visits will equate to 26 weeks. If the patient has no evaluable visits or does not have baseline data they will be censored at day 1 unless they die within 2 visits of baseline (16 weeks plus 1 week allowing for a late assessment within the visit window).

The population for analysis of time to symptom deterioration will include a subset of the ITT population who have baseline scores ≤ 90 .

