3.3.2.1 Time to symptom deterioration

For each of the symptoms scales/items in EORTC-QLQ-LC-13, time to symptom deterioration will be defined as the time from the date of randomisation until the date of the first clinically meaningful symptom deterioration (an increase in the score from baseline of ≥ 10) or death (by any cause) in the absence of a clinically meaningful symptom deterioration, regardless of whether the patient withdraws from study treatment or receives another anticancer therapy prior to symptom deterioration (i.e. date of symptom deterioration event or censoring – date of randomisation + 1). Death will be included as an event only if the death occurs within 2 visits of the last PRO assessment where the symptom change could be evaluated.

Patients whose symptoms (as measured by EORTC-QLQ-LC-13) have not shown a clinically meaningful deterioration and who are alive at the time of the analysis will be censored at the time of their last PRO assessment where the symptom could be evaluated. Also, if symptoms progress after 2 or more missed PRO assessment visits (using the same definitions for two missed visits as used in the ‘Time to symptom deterioration’ derivation in Section 3.3.1) or the patient dies after 2 or more missed PRO assessment visits, the patient will be censored at the time of the last PRO assessment where the symptom could be evaluated. If the patient has no evaluable visits or does not have baseline data they will be censored at day 1 unless they die within 2 visits of baseline (16 weeks plus 1 week allowing for a late assessment within the visit window).

The population for analysis of time to symptom deterioration will include a subset of the ITT population who have baseline scores ≤ 90 as a worsening of 10 points is not possible with a baseline value of >90 .

In the analysis, RECIST 1.1 progression will not be considered as symptom deterioration and data will not be affected by RECIST progression.

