4.2.3 Secondary patient reported outcome endpoints

The PRO endpoints that have been identified as primary are EORTC QLQ-C30 time to HRQoL deterioration for global health status and LC13 time to symptom deterioration for each of dyspnoea, cough, haemoptysis, and chest pain. These are not part of the main multiple testing procedure and as supportive endpoints will need a Bonferroni adjustment to the significance level to aid interpretation. Therefore, these 5 endpoints will be tested at a 1% significance level and 99% CIs will be produced.

The other time to symptom deterioration endpoints will be tested at a 5% significance level and 95% CIs will be produced.

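### For the five key PRO time-to-deterioration endpoints, the rule for deterioration after two missed questionnaires omits the pre-gap limit on the censoring date, so read literally it censors on or after the recorded event

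*Protocol*

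**What the plan says.** SAP 4.2.3 names five key PRO endpoints: time to deterioration in QLQ-C30 global health status and in LC13 dyspnoea, cough, haemoptysis and chest pain. On their testing it says: "Therefore, these 5 endpoints will be tested at a 1% significance level and 99% CIs will be produced".

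The censoring date for a patient who deteriorates after two or more missed PRO visits is given in these places:

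- **Protocol 11.3.1.2 (LC13), SAP 3.3.1.2 (global health status and function) and SAP 3.3.2.1 (LC13):** "the patient will be censored at the time of the last PRO assessment where the symptom could be evaluated". No limit follows.
- **Protocol 11.3.1.1, QoL/function:** the date is again that of the final evaluable form, and the text runs straight on to another rule: "where QoL/function could be evaluated. If a patient has no evaluable visits or does not have baseline data they will be censored at Day 1". No limit is attached to the date. The QLQ-C30 symptom paragraph of the same section is also unlimited.
- **SAP 3.3.1.1 (QLQ-C30 symptoms):** the last PRO assessment "where the symptom could be evaluated (prior to the two missed assessment visits").
- **SAP 3.2.1.2 (PFS):** "the patient will be censored at the time of the latest RECIST 1.1 assessment prior to the two missed visits". Protocol 11.1.3.2 (PFS), Protocol 11.1.10 (TTDM) and SAP 3.2.2.7 (TTDM) also place the date before the missed visits.

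SAP 3.3.1.2 and 3.3.2.1 refer back to the symptom-deterioration derivation, but only for what counts as two missed visits ("using the same definitions for two missed visits as used in the" earlier derivation). They do not expressly take over its censoring date.

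**The concern.** A deterioration can only be recorded on an evaluable form. For a patient who deteriorates after a gap, the last evaluable form is therefore the deteriorating form or a later one. Later forms are to be expected: under Protocol Table 2, patients who are off drug without confirmed progression keep completing questionnaires every 8 weeks to week 48 and every 12 weeks after that, until confirmed PD. In the protocol, the sentence just before the rule uses the same phrase for patients who have not deteriorated, where it means the final form.

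Followed literally, the rule removes the event and keeps the patient in the risk set as event-free through the gap and through any follow-up after the recorded deterioration. The QLQ-C30 symptom scales would then be censored by one rule and the five key endpoints by another. Two programmers, one following SAP 3.3.1.1 and the other SAP 3.3.2.1, would produce different datasets. The time-to-event analyses planned in the SAP would not show the difference. SAP Table 8 lists only a stratified log-rank test for these endpoints, although Protocol Table 15 still lists an attrition sensitivity analysis.

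**Working it through.** **1. The plan's own figures.** Two missed visits are defined as 2 × visit interval + 1 week early + 1 week late (formula in SAP 3.2.1.2, limits repeated in SAP 3.3.1.1: "then two missing visits will equate to 18 weeks since the previous PRO assessment, allowing for early and late visits").

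- 8-weekly period: 2 × 8 + 2 = 18 weeks
- transition, average interval 10 weeks: 2 × 10 + 2 = 22 weeks
- 12-weekly period: 2 × 12 + 2 = 26 weeks

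All three match the SAP. The Bonferroni level, 0.05 / 5 = 0.01, also matches.

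**2. One patient under both readings.** Evaluable forms at weeks 8 and 16, forms at weeks 24 and 32 missed, deterioration first recorded at week 40. The distance is 40 − 16 = 24 weeks, which exceeds 18, so the rule applies. With the limit from SAP 3.3.1.1, censoring is at week 16 in every row.

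| Last evaluable form | Literal date | Later than pre-gap date | Time after the recorded deterioration counted as event-free |
|---|---|---|---|
| week 40 | week 40 | 24 weeks | 0 weeks |
| week 48 | week 48 | 32 weeks | 8 weeks |
| week 72 | week 72 | 56 weeks | 32 weeks |

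The literal date is never before the deterioration. It coincides with it when the deteriorating form is the last one.

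**3. Death branch.** A patient who dies after two or more missed visits has no form after the gap. The last evaluable form is the pre-gap form under either reading, so nothing changes.

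**4. How many patients.** The documents give no missed-form rate, so this is illustrative. Assumptions: exponential time to deterioration with median 26 weeks, exponential PRO follow-up with mean 80 weeks, forms every 8 weeks to week 48 and then every 12 weeks to week 96, forms missed independently, with or without an added two-visit gap in 15% of patients, and 20,000 patients per scenario.

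| Forms missed | Added gap | Patients affected | Of these, last form later than deterioration | Mean shift in censoring date |
|---|---|---|---|---|
| 5% | none | 0.5% | 87.1% | 54.1 weeks |
| 5% | 15% | 2.8% | 85.5% | 60.7 weeks |
| 15% | none | 3.2% | 82.6% | 56.8 weeks |
| 15% | 15% | 5.1% | 83.7% | 59.0 weeks |
| 25% | none | 6.8% | 82.4% | 58.7 weeks |
| 25% | 15% | 9.1% | 80.6% | 58.7 weeks |

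The SAP limits were applied as written. After a week-48 form (study day 48 × 7 + 1 = 337) the 22-week limit applies, and 72 − 48 = 24 weeks, so there one missed form already counts as two.

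**5. Effect on Kaplan-Meier estimates.** A second simulation assumed median PFS of 56 weeks, forms to progression plus 4 weeks, and median time to deterioration of 26 or 52 weeks. With 15–25% of forms missed, the deterioration-free proportion under the literal rule was higher than under pre-gap censoring by 0.8–4.9 points at 12 months and 2.6–10.1 points at 24 months (2.7–7.9% of patients affected). With 5% missed, about 0.5% of patients were affected and the 24-month difference was under 1 point.

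**The case against.** The strongest reply is that pre-gap censoring is what the plan means.

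- The protocol's QLQ-C30 symptom sentence is as unlimited as the others, and SAP 3.3.1.1 implements it with the limit. That is the sponsor's own interpretation of the wording.
- Deterioration and death share one sentence and one censoring date, and for death the date is the pre-gap form.
- SAP 3.3.1.2 still says symptom inside the HRQoL section, which suggests a sentence carried over with its parenthesis lost.
- The imported definition counts weeks since the previous assessment, so applying it already requires the pre-gap form to be identified.
- Every parallel rule for PFS and TTDM is pre-gap.

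This stands as evidence of intent. It does not change what the two SAP sections say, and they take over only the definition of missed visits.

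The size can also be challenged, and that largely stands. Protocol 6.5 asks for a missed questionnaire to be given at the next visit, and dosing visits are every 2 weeks, so many gaps on treatment would be closed. None of the simulations allows for this. If half of all missed forms were made up, the chance of two consecutive misses under independence would fall to 0.5 × 0.5 = one quarter. Patients off treatment would benefit less.

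A reader might infer that the rule always credits time in a known deteriorated state. The documents do not support that. The deteriorating form may be the last one. The event is also a first change of at least 10 points with no confirmation, so later forms may show recovery.

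**Conclusion.** The point holds as a drafting inconsistency that should be corrected. For all five key PRO endpoints the written rule, taken literally, gives a censoring date on or after the recorded deterioration. This conflicts with SAP 3.3.1.1 and with the probable intent. Neither document says outright that post-event censoring is the chosen rule, and it should not be reported as such.

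The size depends on an unknown missed-form rate. Across the assumed scenarios it runs from under 1% to about 9% of patients, and less where missed forms are made up. The direction is upward for Kaplan-Meier deterioration-free estimates and medians. The hazard ratio hardly moves when missingness is equal by arm. Unequal missingness could bias it, but that bias has not been quantified.

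A reader might infer a threat to the trial's main conclusions; the documents give no ground for that. These endpoints are supportive and outside the main multiple testing procedure, and OS, PFS, power and type I error control are untouched. The mixed-model analyses in SAP 4.2.3.3 (which cover four of the five, not haemoptysis), the visit-level summaries and the compliance rates do not use this censoring rule.

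**What to change.** Add the parenthesis already used in SAP 3.3.1.1, "prior to the two missed assessment visits", to the censoring sentence in five places:

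1. SAP 3.3.1.2 (where symptom should also be changed to HRQoL/function)
2. SAP 3.3.2.1
3. Protocol 11.3.1.1, time to symptom deterioration
4. Protocol 11.3.1.1, time to QoL/function deterioration
5. Protocol 11.3.1.2, time to symptom deterioration

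The protocol synopsis states that the planned analyses had concluded by Amendment 07. The sponsor should therefore also confirm that the programmed censoring date was the pre-gap one, and rerun these endpoints if it was not. The cost is one phrase in five sentences and a check of the derivation code. No new data are needed.

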### **Symptom improvement rate**

The symptom improvement rate will be defined as the number (%) of patients with 2 consecutive assessments at least 14 days apart that show a clinically meaningful improvement (a decrease from baseline score  $\geq 10$  for LC13 symptom scales/items) in that symptom from baseline.

The denominator will consist of a subset of the ITT population who have a baseline symptom score of  $>10$ .

#### **11.3.1.3 Calculation or derivation of health state utility (EQ-5D-5L)**

The EQ-5D-5L index comprises 5 dimensions of health (mobility, self-care, usual activities, pain/discomfort and anxiety/depression). For each dimension, respondents select which statement best describes their health on that day from a possible 5 options of increasing levels of severity (no problems, slight problems, moderate problems, severe problems and unable to/extreme problems). A unique EQ-5D health state is referred to by a 5 digit code allowing for a total of 3125 health states. For example, state 11111 indicates no problems on any of the 5 dimensions. These data will be converted into a weighted health state index by applying scores from EQ-5D value sets elicited from general population samples (the base case will be the United Kingdom valuation set, with other country value sets applied in scenario analyses). Where value sets are not available, the EQ-5D-5L to EQ-5D-3L crosswalk will be applied (Oemar and Janseen 2013). In addition to the descriptive system, respondents also assess their health on the day of assessment on a visual analogue scale, ranging from 0 (worst imaginable health) to 100 (best imaginable health). This score is reported separately.

